5.7.2	. Actigraphy	27
5.7.2	.1 Analysis	27
5.7.3	. Biomarkers	28
5.7.4	. Definition of Subgroups	28
6.	SUPPORTING DOCUMENTATION	29
6.1.	Appendix 1 List of Abbreviations	29
6.2.	Appendix 2 Changes to Protocol-Planned Analyses	
6.3.	Appendix 3 Demographics and Baseline Characteristics	32
6.4.	Appendix 4 Protocol Deviations	33
6.5.	Appendix 5 Prior and Concomitant Medications	
6.6.	Appendix 6 Adverse Events of Special Interest	35
6.7.	Appendix 7 Medications of Special Interest	36
6.8.	Appendix 8 Criteria for Treatment-emergent Markedly Abnormal Laboratory Values	37
6.9.	Appendix 9 Analyses for Assessing and Mitigating the Impact of COVID-19 on Study	-
	Outcome	39
7.	REFERENCES	40

VERSION HISTORY

Table – SAP version History Summar	Table	- SAP	Version	History	Summary
------------------------------------	-------	-------	---------	---------	---------

SAP Version	Approval Date	Change	Rationale
1.0	08/15/22		
2.0	09/07/2023	1.1: Updated CDR cutoff for population from 2 to 1	Change is consistent with protocol amendment
		5.1.1: Updated Visit Window for MMSE	Added baseline and Day 43 windows to be consistent with schedule of activities for MMSE and windows for other parameters
		5.3.1: Clarified the data usage rules regarding ICE strategies for the estimands	Updated rules to remain consistent with other studies in the program
		5.3.2, 5.3.3: Clarified rescue medication ICE	Existing wording did not specify how to handle rescue medication occurring after treatment discontinuation
		5.3.2, 5.5.7, 5.5.10: Removed community dwelling/assisted living status as factors from MMRM/ANCOVA models	Insufficient numbers of participants were stratified to each of the levels to include as a factor in models
		5.3.2, 5.5.7, 6.3: Changed primary models to use per-eDC values of stratification factors, rather than per-IWRS values	Significant mis-stratification based on these stratification factors was observed. Study team agreed that per-eDC values should be used for primary analysis
		5.3.2.1.1: Added that in the case that a structured covariance matrix needs to be used, a robust sandwich variance estimator will be used.	Change to remain consistent with health authority feedback for other studies in the program
		5.3.4: Section added to describe sensitivity analyses related to use of per-eDC vs per-IWRS values of stratification factors	Given that primary analysis was changed to use per-eDC values, a sensitivity analysis based on per-IWRS values was desired
		5.4.1.2.2, 5.5.5.2, 5.5.8.1: Clarified that both SDI summary scores should be used.	Two different SDI summary scores exist. Both are of interest. Existing wording did not specify that both should be included

	unit)	Statistica	l Analysis Plan 42847922ALZ2001
		5.5.1.2: Remove Change from Baseline in NPI-12 Caregiver Distress Score MMRM analysis	Team agreed that means and mean changes in Caregiver Distress over time were sufficient for exploration of this endpoint
		5.5.5.2: Specified the exact NPI- C analyses to be performed for rebound analysis	Specified sub-totals are of more interest for this study than total score
		5.6.3.1: Added Shift in Metabolic Lab value table	To assist in clinical understanding of treatment
		5.6.3.1, 5.6.3.3: Clarified that only DB Lab and ECG values may be TE.	Clarifying that post- discontinuation of treatment labs would not be considered TE
		5.7.2.1: Actigraphy section updated to specify mobility parameters to be analyzed, and to specify analyses performed to explore correlations	After seeing the parameters included in actigraphy data, the team agreed upon exact parameters to analyze, and analyses to perform
		5.7.4: Added Baseline NPI-12 Sleep Doman Score, Age Group II, and BMI to listing of Subgroups	Updated subgroups of interest based on team consensus
		6.1: Added eCOA abbreviation to abbreviation table	For clarification
		6.3: Removed Prior Medications of Special Interest from Baseline Disease Characteristics table. Added baseline CDR score.	Prior Medications of Special Interest to be included in a separate output. Baseline CDR added to observe impact of protocol amendment
		6.8: Updated several markedly abnormal thresholds for hematology variables to be expressed in Fraction of 1, rather than %. Updated lab test names. Updated Vitamin B12 limits to be expressed in correct units.	Updates made to align table with structure of received data
3.0	11/14/2023	5.4.1.1.1	Clarified the calculation of CMAI-C total score
		5.6.3.1	Team decision to produce shift in lab value table for all chemistry labs. Added categories for metabolic lab shifts

1. INTRODUCTION

This statistical analysis plan (SAP) contains definitions of analysis sets, derived variables, and statistical methods for all planned analyses for study 42847922ALZ2001.

1.1. Objectives and Endpoints

For the following objectives and endpoints, probable AD with clinically significant agitation/aggression is defined as: Diagnostic and Statistical Manual of Mental Disorders-5th Edition (DSM-5) diagnosis of probable Alzheimer's Disease (AD) and criteria of a syndrome diagnosis of agitation based on International Psychogeriatric Association (IPA) consensus clinical and research definition of agitation in cognitive disorders, have an MMSE total score from 10 to 24 (inclusive), and a Clinical Dementia Rating (CDR) of ≥ 1 . Additionally, patients will be characterized by the presence of clinically significant agitation/aggression defined as NPI-12 agitation/aggression (A/A) domain score ≥ 4 with NPI frequency score ≥ 2 at entry and baseline with no more than 35% of improvement allowed in NPI-12 A/A score during the screening period.

Double-blind Treatment Phase

Objectives	Endpoints			
Efficacy				
Primary				
• To investigate the effect of seltorexant versus placebo on the sum of agitation and aggression domain scores (A+A) of the Neuropsychiatric Inventory - Clinician rating (NPI-C) in participants with probable AD with clinically significant agitation/aggression.	• Change from baseline to Day 43 on NPI- C A+A scores.			
Secondary –Efficacy				
To investigate the effect of seltorexant versus p probable AD with clinically significant agitatio	lacebo on the following in participants with n/aggression:			
Cohen-Mansfield Agitation Inventory community version (CMAI-C) total score	• Change from baseline to Day 43 on the total CMAI-C score.			
• Sleep symptoms as assessed by the Sleep Disorder Inventory (SDI).	• Change from baseline to Day 43 on SDI total score.			
Secondary – Pharmacokinetics				
• To investigate the plasma pharmacokinetics (PK) of seltorexant and its M12 metabolite in participants with probable AD with clinically significant agitation/aggression.	• Plasma concentrations of seltorexant and its M12 metabolite at Day 15 and Day 43.			

Statistical Analysis Plan 42847922ALZ2001

Objectives	Endpoints					
Exploratory – Digital						
To investigate the effect of seltorexant versus p	lacebo on the following in participants with					
probable AD with clinically significant agitatio	n/aggression:					
• Sleep and activity metrics using an	• Change from baseline on sleep and					
actigraphy device.	activity metrics.					
• Sleep and mobility using an off-body	• Change from baseline on sleep and					
touchless sensor in a subset of	mobility measurements.					
participants, (if feasible and available)						
Exploratory –Biomarkers						
• To investigate the effect of seltorexant	• Change from baseline in levels of blood					
versus placebo in participants with	biomarkers of AD					
probable AD with clinically significant						
agitation/aggression on blood biomarkers						
including but not limited to:						
o biomarkers of AD, eg, p217+tau, A β_{1-}						
42/40 levels and ratio, NfL, and other						
exploratory biomarkers						
Other Exploratory						
To investigate the effect of seltorexant versus p	lacebo on the following in participants with					
probable AD with clinically significant agitatio	n/aggression:					
• Variables derived from the NPI-12/NPI-C	• Change from baseline over time on the					
rating:	specified NPI-12/NPI-C variables.					
• The sum of the NPI-C delusion and						
hallucination domain scores (NPI-C						
D+H)						
• Individual NPI-C domain scores for						
agitation, aggression, dysphoria,						
delusions, and hallucinations						
• NPI-12 total score						
• NPI-12 Caregiver Distress total score						
• All NPI-12 individual item scores						
SDI Caregiver Distress score	• Change from baseline over time in SDI					
	caregiver distress					
• Short-term rebound effects on behavioral	Change in Physician Withdrawal					
and psychological symptoms of dementia	Checklist (PWC-20) from End of DB					
(BPSD) as well as withdrawal symptoms	Treatment/EW to first follow up visit.					
	• Change in NPI-12, NPI-C and SDI scores					
	from End of DB Treatment/EW to first					
	follow up visit.					
CMAI-C factor scores	Change from baseline over time on					
	CMAI-C factor scores.					
• Depressive symptoms as assessed by the	Change from baseline on GDSI Total					
Geriatric Depression Scale, Informant	score at Day 43.					
version (GDSI).						

Statistical	Analysis	Plan	42847922AL 72001
Statistical	Analysis	I Iall	4204/722ALL2001

Objectives	Endpoints			
• The association between treatment effect of seltorexant in sleep and treatment effect	• Correlation between change in NPI-C A+A and change in SDI total score, and			
in agitation/aggression	mediation effect on change in NPI-C A+A through change in SDI total score			
Cognitive symptoms	• Change from baseline to Day 43 on Alzheimer's Disease Assessment Scale Cognitive subscale 14-item version (ADAS-Cog-14) composite cognitive score and from screening to Day 43 on the Mini-Mental State Examination (MMSE) total score.			
Safety				
To investigate the effect of seltorexant versus p probable AD with clinically significant agitatio	lacebo on the following in participants with n/aggression:			
• Safety and tolerability of seltorexant	• Change from baseline in Vital signs, Clinical Labs (chemistry, hematology, urinalysis), ECG, C-SSRS, and Treatment Emergent Adverse Events (TEAEs) including AEs of special interest (AESI).			

Statistical hypotheses pertaining to the primary endpoint are described in Section 2.

Descriptive analysis of pharmacokinetic data is described in section 5.7.1. Details about further analysis of biomarker and pharmacokinetic data pertaining to the additional exploratory objectives will be described in their respective analysis plans separately.

1.2. Study Design

This is a multicenter, DB randomized, parallel-group, placebo-controlled, 6-week study to assess the efficacy and safety of seltorexant 20mg in participants aged 55 to 85 years, inclusive, with probable AD with clinically significant agitation/aggression.

This study will consist of 3 phases: a screening phase (up to 28 days), a double-blind treatment phase (43 days), and a post-treatment follow-up phase (14 days after DB treatment phase).

Approximately 86 participants with probable AD and clinically significant agitation/aggression will be randomly assigned to receive placebo or seltorexant 20 mg in a 1:1 ratio for 6 weeks in the DB treatment phase. Randomization will be stratified by baseline NPI-12 sleep domain score (<4, ≥4) and community dwelling/assisted living.

Participants who discontinue early from study intervention in the DB treatment phase will be further assessed during additional follow-up visits every 2 weeks until Day 57.

Statistical Analysis Plan 42847922ALZ2001

Participants will take their assigned study intervention at home, once daily at bedtime during DB treatment phase.

2. STATISTICAL HYPOTHESES

This study is designed to show that the treatment effect in improving agitation and aggression (as measured by change from baseline on Day 43 in NPI-C A+A score) of seltorexant 20 mg is superior to placebo in participants with probable AD with clinically significant agitation/aggression.

If μ_T is the mean change in NPI-C A+A total score for seltorexant group and μ_P is the mean change in NPI-C A+A total score for the placebo group, then the hypothesis can be written as follows:

 $\begin{array}{l} H_0: \, \mu_T \! - \! \mu_P \! \geq \! 0 \, \mathrm{vs.} \\ H_1: \, \mu_T \! - \! \mu_P \! < \! 0 \end{array}$

Superiority can be concluded if the two-sided p-value for the testing of the hypothesis above is less than 0.20.

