9.1. Statistical Hypotheses

This study is designed to show that the treatment effect in improving agitation and aggression (as measured by change from baseline on Day 43 in NIPC A+A score) of seltorexant 20 mg is superior to placebo in participants with probable AD with clinically significant agitation/aggression.

If μ_T is the mean change in NPI-C A+A for seltorexant 20 mg group and μ_P is the mean change in NPC A+A for the placebo group, then the hypothesis can be written as follows:

 $H_0: \mu_T - \mu_P \ge 0 \text{ vs.}$ $H_1: \mu_T - \mu_P < 0$

Superiority in seltorexant 20 mg can be concluded if the one-sided p-value for the testing of the hypothesis above is less than 0.1 (equivalently, the two-sided p-value for the testing of the hypothesis above is less than 0.2, with greater improvement in the 20 mg group).

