3. SAMPLE SIZE DETERMINATION

Assuming a treatment difference of 5 points in change from baseline in NPI-C A+A score between seltorexant 20 mg and placebo, a standard deviation of 10 (effect size of 0.5), and a 15% drop-out rate during the 6-week double-blind phase, 86 participants (randomized in 1:1 ratio to placebo and seltorexant 20 mg) will need to be enrolled in the double-blind phase, in order to achieve 80% power to detect treatment difference, at one-sided 0.1 significance level.

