5.3.1. Definition

The primary efficacy endpoint is the change in NPI-C A+A score from baseline (DB) to Day 43.

The Neuropsychiatric Inventory-Clinician Rating (NPI-C) (de Medeiros 2010) is an instrument that

Statistical Analysis Plan 42847922ALZ2001

expands upon the items and 12 symptom domains of the original NPI. The modified rating methodology of the NPI-C incorporates the expert clinician's impressions to the data provided by the patients and caregivers. For each domain, the domain score will be calculated as the sum of clinician severity ratings (from 0=does not occur to 3=severe) for each item. NPI-C A+A score is the sum of the domain scores from the Agitation and Aggression domains at a given time point, and ranges from 0 to 63. Higher scores represent a more serious condition.

Negative changes in NPI-C A+A represent improvement.

Two estimands are defined for the primary endpoint: The primary estimand is Estimand 1, and the supplementary estimand is Estimand 2.

The sections below describe the primary analyses performed for each primary and supplementary estimand. For treatment policy strategy, data collected after participants experienced intercurrent events will be included in analyses; for hypothetical strategy, data collected after participants experienced an intercurrent event of treatment switch will not be included in analyses. Otherwise, data observed up to and including DB disposition day will be included.

5.3.2. Estimand 1

Estimand 1 will be the **primary estimand**. The analysis will be performed on the full analysis set.

Primary Trial Objective: To evaluate the efficacy of seltorexant 20 mg compared with placebo in improving agitation/aggression symptoms in participants with probable AD with clinically significant agitation/aggression.

Estimand Scientific Question of Interest: What is the benefit in improving agitation/aggression symptoms from seltorexant 20 mg versus placebo in adults and elderly participants with probable AD with clinically significant agitation/aggression based on the change from baseline in NPI-C A+A score if the participants take study intervention as directed?

Estimand 1 is defined by the following 5 components:

Study Intervention:

- Experimental: Seltorexant dose of 20 mg
- Control: Placebo

Population: Participants with probable AD with clinically signification agitation/aggression, as reflected by the inclusion/exclusion criteria.

Variable: Change in NPI-C A+A total score from baseline to Day 43

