5.3.2.1. Analysis Methods

5.3.2.1.1. Primary Analysis

Descriptive statistics of the actual values and the change from baseline (DB) to each postbaseline time point will be presented for NPI-C A+A score by intervention group.

NPI-C A+A score will be analyzed by a Mixed-Effect Model for Repeated Measures (MMRM) based on observed case. The fixed terms included in the model will be intervention group, baseline NPI Sleep domain score category (per eDC), time, and time-by-intervention interaction, and baseline (DB) NPI-C A+A total score as a covariate. The within-subject covariance between visits will be estimated via an unstructured variance-covariance matrix. In case of convergence problems, alternative variancecovariance structures will be tried in the following order, with the first structure that converges being used in the analysis: heterogeneous Toeplitz, standard Toeplitz, and AR(1) with separate subject random effect; in addition, a robust sandwich variance estimator will be used to address the potential impact of covariance matrix misspecification on the estimation and testing of treatment effect. The Kenward-Roger method will be used for approximating the denominator degrees of freedom. Comparison between seltorexant and placebo at Day 43 will be performed using the appropriate contrast. Difference in least square means and 2-sided 80% CI will be presented.

Least squares mean changes from baseline(DB) (+/- SE) will be presented graphically over time.

No multiplicity adjustment will be included for efficacy endpoints.

5.3.3. Estimand 2

Estimand 2 will be a **supplementary estimand**. The analysis will be performed on the full analysis set.

All components as described under Estimand 1 (Section 5.3.2) apply to Estimand 2 except for the strategy for addressing intercurrent events.

Intercurrent events and their corresponding strategies:

	Statistical Analysis Plan 42847922ALZ2001
	Name of Strategy for Addressing Intercurrent
Intercurrent Events	Events and Its Description
1. Treatment discontinuation of study drug	Treatment policy strategy: all observed values of
without switching	the endpoint are used regardless of whether or not
	the participant had experienced this intercurrent
	event
2. Switch of treatment	Hypothetical strategy: as if the intercurrent event
	had not occurred
3. Allowed rescue medication	Treatment policy strategy: all observed values
(including use after treatment	of the endpoint are used regardless of whether

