5.5.8.1. Analysis

Correlations between change in NPI-C A+A score and change in SDI average total score and between change in NPI-C A+A score and change in SDI summed product score over time will be explored; Pearson and Spearman correlation coefficients will be calculated. Scatter plot of change in scores of the 2 assessment scales over time will be presented for each intervention group.

A mediation analysis will be performed to examine the mediating role of improvement in sleep assessed by change from baseline in SDI score on change from baseline in NPI-C A+A score provided that both endpoints demonstrate a statistically significant difference between seltorexant and placebo. This analysis will assess the extent to which change in NPI-C A+A score may be mediated by or independent of change in SDI score based on observed data (i.e., data collected at each time point without carrying forward previous values) at Day 43. The analysis will consider both change in NPI-C A+A score and change in SDI score as continuous variables.

• Simulation-based Counterfactual Approach: this analysis introduced by Imai et. al obtains the natural direct effect and natural indirect effect using numerical simulations. The approach uses parametric bootstrapping to construct the point estimate and its uncertainty estimates for direct effect and indirect effect from the bootstrap sampling distribution. For each bootstrapped sample, change from baseline in NPI-C A+A score and change from baseline in SDI score will be analyzed. The ANCOVA analysis of change in NPI-C A+A score from baseline will include factors for treatment (placebo and seltorexant dose groups), change from baseline (Day 1, predose) in SDI score, treatment-by-change from baseline in SDI score

Statistical Analysis Plan 42847922ALZ2001

interaction if the interaction is significant, and baseline NPI-C A+A score as a covariate. The ANCOVA analysis of change in SDI score will include factors for treatment (placebo and seltorexant dose groups), and baseline NPI-C A+A score as a covariate. Estimate of the controlled direct effect will be obtained by plugging in the estimated coefficient values and the mean level of change in SDI score into the analytic expressions.

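### Does the SAP's two-sided p<0.20 success rule, which lacks the protocol's direction clause, let a placebo-favouring result count as superiority?

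*SAP*

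**What the plan says.** Protocol section 9.1 states the primary success rule in two forms. The first is one-sided: "Superiority in seltorexant 20 mg can be concluded if the one-sided p-value for the testing of the hypothesis above is less than 0.1". The second, given as its equivalent, is two-sided with a condition on direction: "the two-sided p-value for the testing of the hypothesis above is less than 0.2, with greater improvement in the 20 mg group".

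SAP section 2 opens with the aim of showing that the treatment effect "of seltorexant 20 mg is superior to placebo in participants with probable AD with clinically significant agitation/aggression". It sets out H0: μ_T − μ_P ≥ 0 against H1: μ_T − μ_P < 0, and then gives the rule: "Superiority can be concluded if the two-sided p-value for the testing of the hypothesis above is less than 0.20". Neither the one-sided form nor the direction condition is in that sentence.

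Other parts of the SAP bear on how to read it:

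- Section 3 gives the sample size "at one-sided 0.1 significance level".
- Section 5.3.1 fixes the sign of the scale: "Negative changes in NPI-C A+A represent improvement".
- Section 5.3.2.1.1 specifies the output for the Day 43 contrast: "Difference in least square means and 2-sided 80% CI will be presented".
- Section 5.5.8.1 allows the exploratory mediation analysis "provided that both endpoints demonstrate a statistically significant difference between seltorexant and placebo".

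**The concern.** A two-sided p-value carries no sign. A rule of two-sided p<0.20 equals a rule of one-sided p<0.10 only if the estimate must also lie on the favourable side, and the protocol adds its clause for that reason. SAP section 2 is where the SAP states the primary success rule, and the clause is missing there. Neither the primary analysis section nor the mediation condition states a direction, and the SAP version history lists no change to section 2 that would explain the difference.

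If the sentence were applied as a threshold alone, a sufficiently large difference in favour of placebo would satisfy it. The nominal error rate would be 0.20 rather than the planned 0.10, and the SAP would disagree with both the protocol and its own section 3.

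**Working it through.** **Inputs** (SAP section 3, identical in protocol 9.2): difference 5 points, SD 10, drop-out 15%, 1:1 allocation, 86 participants, 80% power, one-sided 0.1.

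**1. The plan's own figure.** Normal approximation, per arm:

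n = 2 × [SD × (z₀.₉₀ + z₀.₈₀) / δ]² = 2 × [10 × (1.2816 + 0.8416) / 5]² = 36.06

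With drop-out: 36.06 / 0.85 = 42.43, so 43 per arm and 86 in total. The stated figure reproduces.

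This does not separate the two wordings, because one-sided 0.1 and two-sided 0.2 share the critical value 1.2816. It rules out only a one-sided 0.20 test, which would need 2 × [10 × (0.8416 + 0.8416) / 5]² / 0.85 = 26.7 per arm, or about 54 in total. Neither document proposes that test.

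**2. Critical difference.** Evaluable per arm: 86 × 0.85 / 2 = 36.55. SE = 10 × √(2/36.55) = 2.339. With 71 degrees of freedom t₀.₉₀ = 1.2936, so the critical difference is 1.2936 × 2.339 = 3.03 points. The protocol rule is met when the estimate (seltorexant minus placebo) is below about −3.03. The bare threshold is also met above +3.03.

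**3. Probabilities at zero true difference.**

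| Event | Probability |
|---|---|
| two-sided p<0.20, estimate favours seltorexant | 0.10 |
| two-sided p<0.20, estimate favours placebo | 0.10 |
| two-sided p<0.20, either direction | 0.20 |

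Only the first row is a false claim that seltorexant is superior. The second becomes one only if a result favouring placebo is labelled superiority of seltorexant.

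**4. A hypothetical case.** Suppose placebo were truly better by 2.5 points. This is an assumption and stands in neither document. The noncentral t distribution gives 0.413 for p<0.20 in placebo's favour and 0.010 in seltorexant's, 0.423 in all (0.425 by the normal approximation). Almost all of it is again the event that would have to be mislabelled.

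**5. What the sentence tests.** The p-value is for the hypothesis printed above it, whose alternative is μ_T − μ_P < 0. When the estimate is negative, the one-sided p for that alternative is half the two-sided p. When it is positive, the one-sided p is 1 minus half the two-sided p. A placebo-favouring result with two-sided p<0.20 therefore has a one-sided p above 1 − 0.10 = 0.90 for the stated alternative. It lies inside H0 and gives no support to H1.

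**6. What is reported.** The difference in least-squares means and its two-sided 80% interval show the direction. An upper limit below zero is the same condition as one-sided p<0.10 in favour of seltorexant, so the planned table already displays the protocol's rule.

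**7. Power.** At a true benefit of 5 points, with 36.55 per arm, power in seltorexant's favour is 0.804 by the normal approximation. The opposite tail adds 0.0003. The wording makes no practical difference.

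**The case for a change.** The best case for a change is that a prespecified success rule should be executable as written, without combining passages. Protocol section 9 leaves the specific details to the SAP, and the SAP sentence asks for a two-sided p-value for a one-sided hypothesis, which is loose. The protocol's authors thought the direction clause worth writing. The mediation condition in SAP 5.5.8.1 also speaks of a significant difference without direction, so the wording recurs. Restoring the clause would cost a few words.

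Part of this stands. The two documents differ in wording, and the protocol's version is the more exact. But the passages to be combined are adjacent: the alternative hypothesis is in the same section as the rule, and the one-sided level is in the next. The mediation condition does not state the success rule. It governs an exploratory analysis, described there as examining the mediating role of improvement in sleep, so benefit is its context. The worst outcome there is an extra exploratory table.

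**Conclusion.** The wording differs, but no change to the plan follows. SAP section 2 shortens the protocol's rule and loses a clause that its own hypotheses, the one-sided level in SAP section 3, the sign convention in SAP 5.3.1 and protocol 9.1 all supply. An analyst following these documents would not call a placebo-favouring result superiority of seltorexant.

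The false-superiority rate at zero difference is 0.10 under either wording. The 0.20 and 0.423 figures are probabilities of a small two-sided p-value in either direction, not of an error the trial would make. With the clause or without it, the sample size, power, critical difference, model, estimate and 80% interval are the same.

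This rests on the SAP sentence being read with the hypothesis it names, and on the sign of the estimate being reported, as the SAP provides. The 3.03-point figure also assumes the design SD of 10 and 15% drop-out.
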